Background: In a variety of visual search experiments, both basic and clinical, the data have been consistent with a situation where the variability of the signal (or target) is greater than the variability of the noise (distractors). As an example, in screening for breast cancer, this would mean that the variability of backgrounds in mammograms would be less than the variability in actual signs of cancer (the signal in these “signal detection theory” (SDT) terms. The classic sign of this greater signal variability is a “zROC” function with a slope < 1 – typically around 0.6. A slope of 1.0 is indicative of an equal variance 2AFC task; that is, the same amount of variability in the signal and the noise. The present experiment is part of a series where we systematically vary the parameters of a simple 2-alternative forced-choice (2AFC) task where participants decide if a stimulus is “good” or “bad”. Participants can also be helped by a simulated AI system. This is our **Human-AI Collaboration Tester (HAICT)**.

For the HAICT task that we have been testing in this series of experiments, we would expect equal variance, but we think it would be worth checking so we will systematically vary prevalence which will shift criterion. That will sweep out an ROC curve that we can examine.

We will also test the Second Reader faux-AI in order to determine if low prevalence makes Second Reader worse.

- (H1): We expect to replicate the finding that human criteria become more conservative as prevalence declines.
- (H2): We predict that the slope of the resulting zROC will be 1.0.
- (H3): We hypothesize that low prevalence will make Second Reader AI less effective because the positive predictive value of its comments will be low.

1. **Dependent variable.** Describe the key dependent variable(s) specifying how they will be measured.

The main dependent variables of interest are accuracy (and the signal detection derivatives of accuracy, d' and c), reaction time, and subjective ratings on the survey following each block.

2. **Conditions.** How many and which conditions will participants be assigned to?

This series of experiments investigates how changing the input from a simulated AI can affect the decisions made by human observers in a two-alternative forced choice task (like the decision to recall a woman for further examination in mammography). We have developed a paradigm called the Human-AI Collaboration Tester (HAICT) that allows for efficient testing of interactions between a human and a simulated AI.

The observers' task in all conditions is to give a 2AFC decision about whether a stimulus is "bad" or "not bad." To use language roughly mimicking a medical diagnosis, each stimulus is referred to as a "case." Observers are asked to make a 2AFC decision about arrays of colored shapes. The decision is made based on the predominant color of the case. The number of elements of each color are drawn from one of two normal distributions, one for positive (bad) stimuli and the other for negative (not bad) stimuli.

The results from previous HAICT experiments (3 and 4) showed that human performance in the Second Reader condition drops off significantly at low prevalence. Performance in the Second Reader condition was better than Baseline when the prevalence of bad cases was 50% but was significantly worse than Baseline when prevalence was only 10%. In this experiment, we manipulate the prevalence of "bad" cases in the Second Reader and Baseline conditions. Four different prevalence rates will be tested – 10%, 33%, 67%, and 90%. Observers will complete 8 blocks (2 AI rules x 4 prevalence rates), and block order is random.

AI rules to be tested:

1. Baseline - No AI input. Observer classifies each case as "bad" or "not" bad on their own.
2. Second Reader - The observer makes an initial decision about every case. The AI silently classifies stimuli using a conservative criterion ($c = 0.5$). The logic for the conservative criterion is that the second reader is being used to cut down on false positive responses and so it is intended to question positive human responses that

might be marginal. If the observer and AI disagree, then the AI informs the human observer. The observer is then given a chance to either change their response or go with their first opinion.

As in Experiments 1-5, the AI d-prime is fixed at 2.2. Feedback is known to increase the prevalence effect, so feedback will be given in both the practice and the test trials. Observers will complete 20 practice trials and 200 test trials in each block. Immediately after each block is completed, observers will be shown a summary of their performance. After the Second Reader blocks, they will also be asked to answer three subjective questions about the usefulness of the AI (see "Files" for more details).

3. Analyses. Specify exactly which analyses you will conduct to examine the main question/hypothesis.

First, we summarize the number of hits, true negatives, misses, and false alarms in each block. From this, we can calculate the accuracy, the positive predictive value, sensitivity (d-prime), and the criterion for each observer under each of the different conditions. Given measures of performance at 4 levels of prevalence, we can estimate the ROC curve ($pHit \times pFA$) and the zROC function ($zHit \times zFA$). We will test the hypothesis that the slope of the zROC is equal to 1 (the consequence of an equal variance 2AFC task).

4. More analyses. Any secondary analyses?

We will look to see if the observers' subjective opinions about the AI are correlated with variables such as the empirical d-prime, or the positive predictive value.

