**Figure 2: Construction of HAICT stimuli**

Whether a case is “positive” or “negative” determines the numbers of red and green cells in the stimulus. For a negative trial, the number of red cells is derived from one normal distribution. For positive trials, the number is derived from another distribution with a higher mean. The difference in those means, converted to  $d'$  puts an upper limit on performance. That is, if the distributions are separated by  $d'=2.5$ , as they are in this case, even the most ‘expert’ observer cannot produce results with  $d'$  better than 2.5, except by chance. This method means that some positive cases will look negative and vice versa. It is important to explain this to participants, especially if the experiment involves feedback in order to avoid confusion and frustration.

Human and AI stimuli can be the same or they could be generated separately so that the maximum performance of the two observers can be independently varied. In this experiment, both the AI and human have a maximum performance of a  $d'$  of 2.5.

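### Does the AI d' of 2.2 in the Protocol contradict the 2.5 given in the SAP?

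*Protocol*

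**What the plan says.** The Protocol, in the text under item 2 (Conditions), states: "As in Experiments 1-5, the AI d-prime is fixed at 2.2". It gives the AI a criterion of 0.5 and sets prevalence at 10%, 33%, 67% and 90%. It does not mention a stimulus ceiling.

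The SAP, under Figure 2 (Construction of HAICT stimuli), explains that the distance between the positive and negative distributions "puts an upper limit on performance". It gives that distance with the words "if the distributions are separated by $d'=2.5$ , as they are in this case". It notes that human and AI stimuli may be the same or may be generated separately, and concludes that here "both the AI and human have a maximum performance of a $d'$ of 2.5". It states no achieved or programmed AI d', and the value 2.2 does not appear in it. Its Specific Method section repeats the criterion of 0.5 and the four prevalence levels.

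H3 in the Protocol predicts that "low prevalence will make Second Reader AI less effective because the positive predictive value of its comments will be low". The analyses in Protocol item 3 and in the SAP's Data analysis section are built from each observer's hits, misses, false alarms and true negatives.

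**The concern.** Both documents describe the same experiment, yet one attaches 2.2 to the AI and the other attaches 2.5, without a linking sentence. A human falls below a stimulus ceiling through internal noise. A simulated AI does so only if the program makes it, and neither document describes such a step. Someone reading only the SAP could take the AI to perform at 2.5.

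The AI's skill relative to the human determines how often its comments are right and how much help it could give. If the wrong figure were used to interpret H3, or to judge whether observers made good use of the AI, the conclusion about the AI's value could be off.

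**Working it through.** **Are the two statements compatible?** The SAP sentence gives the human and the AI the same 2.5 and calls it a maximum. Nobody would read it as the human's achieved d', and the same word governs the AI. The only stated operating value is 2.2, which is below 2.5. A simple mechanism would connect them. If independent noise with SD s (in units of the stimulus SD) is added to a signal with separation 2.5, then d' = 2.5/√(1 + s²). Setting this to 2.2 gives s² = (2.5/2.2)² − 1 = 0.291, so s = 0.54. The documents do not say this was done; it shows only that both figures can be true.

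**The plan's own derived figure.** The SAP's Introduction gives an optimal joint d' of about 3.5 for two uncorrelated observers at 2.5 each. √(2.5² + 2.5²) = 3.54, so it reproduces. It is an introductory illustration, not a setting or benchmark for this experiment. It also requires uncorrelated observers. The HAICT methodology section describes stimuli that both observers evaluate; if they judge the same sample, no combination can exceed the ceiling of 2.5 except by chance. Joint-d' comparisons are therefore not a sound measure of what is at stake here.

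**AI predictive value under each figure.** Inputs: d' of 2.2 (Protocol) or 2.5 (SAP ceiling), c = 0.5 (both documents) and the four prevalences p. Assumptions: equal variance, and c measured from the midpoint between the distributions. (The SAP prints c with a difference of z-scores, which would make it −d'/2 and never +0.5; the standard form with the sum is used here.)

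- Hit rate H = Φ(d'/2 − 0.5); false-alarm rate F = Φ(−d'/2 − 0.5).
- d' 2.2: H = Φ(0.60) = 0.726, F = Φ(−1.60) = 0.055.
- d' 2.5: H = Φ(0.75) = 0.773, F = Φ(−1.75) = 0.040.
- PPV = pH / [pH + (1 − p)F].

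| Prevalence | PPV, d' 2.2 | PPV, d' 2.5 | Gap |
|---|---|---|---|
| 10% | 0.595 | 0.682 | 0.087 |
| 33% | 0.867 | 0.905 | 0.038 |
| 67% | 0.964 | 0.975 | 0.011 |
| 90% | 0.992 | 0.994 | 0.003 |

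From 90% to 10% prevalence, PPV drops by 0.40 with d' 2.2 and by 0.31 with d' 2.5. The direction is the same. If c were instead measured from the mean of the negative distribution, PPV at 10% would be 0.256 against 0.260, almost no gap.

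**The quantity H3 refers to.** H3 concerns the AI's comments, which arise only when AI and observer disagree. For a comment that the observer may have missed a positive case, PPV = p(1 − h)H / [p(1 − h)H + (1 − p)(1 − f)F], where h and f are the human hit and false-alarm rates. The documents give no human values, so a range is needed: human d' of 2.2 or 2.5, human criterion either neutral or optimal for the prevalence, and independent noise.

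| Prevalence | AI d' 2.2 | AI d' 2.5 |
|---|---|---|
| 10% | 0.148 to 0.408 | 0.202 to 0.501 |
| 90% | 0.755 to 0.949 | 0.818 to 0.965 |

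The two columns overlap widely, and the assumed human behaviour moves the result more than the AI's d' does. If disagreements in both directions are pooled, the share in which the AI is right moves the other way: at 10% and 90% it is 0.376–0.654 and 0.153–0.317 with AI d' 2.2, and 0.455–0.716 and 0.184–0.374 with AI d' 2.5. That bears on how H3 is worded, but again the pattern is the same for both AI values.

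**Does AI d' feed any planned analysis?** Protocol item 3 derives accuracy, predictive value, d', criterion and the zROC slope from counts. Item 4 correlates subjective opinions with variables such as the empirical d' or the predictive value. The SAP's Data analysis section uses only observed hit and false-alarm proportions. No formula takes the nominal AI d' as an input, and no comparison with an ideal combination is planned.

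**The case for a change.** The best case for a correction is that, in the SAP, the sentence on the 2.5 maximum is the only statement of the AI's skill in this experiment, and it comes straight after the remark that the two observers' maxima can be set independently. A simulated AI has no reason to fall short of its maximum unless noise is built in, and no such step is described. The SAP itself lists the relative skill of human and AI first among the factors that shape the interaction. Neither document alone would let another laboratory rebuild the AI. The remedy is also cheap: the four prevalences sum to 200%, so the 12 analysed observers give 12 × 400 = 4800 positive and 4800 negative Second Reader trials. The standard error of the AI's realised d' is then about 0.035, and a difference of 0.3 would be plain.

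The point about description stands: a sentence relating 2.2 to 2.5 would help a reader. The claim of contradiction does not stand, because it requires the AI to run at its ceiling, which neither document says. Nor does the claim of a faulty benchmark, since none is planned. The realised AI d' would be a useful descriptive figure if the AI's calls were stored, which the documents do not state, but it would alter no planned estimate.

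**Conclusion.** No change to the plan follows. An operating d' of 2.2 and a ceiling of 2.5 are different quantities and can both be true. The largest effect of taking one for the other is 0.087 in the AI's theoretical PPV, at 10% prevalence. That figure covers all the AI's positive calls rather than the comments H3 concerns, and rests on equal variance and a midpoint-referenced criterion. On the narrower quantity the ranges overlap, and in every case the direction with prevalence is the same. The planned estimates of observer d', criterion, predictive value and zROC slope come from counts and are unaffected.

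The gap is one of description: how the AI's decisions are generated, and how 2.2 relates to 2.5. An analyst who needs the AI's characteristics to discuss H3 would take them from the program that produced its calls. This conclusion would change only if an ideal-observer or optimal-combination comparison were added, because the AI's actual d', and whether it shares the human's stimulus sample, would then be inputs.

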## **HAICT methodology**

HAICT treats the human-AI interaction as a signal detection problem with two observers. We generated a set of visual stimuli that both our human and “AI” observer must evaluate. This is analogous to a CADx situation where a human reader might use a CAD system to help determine if a mass is cancerous.

At the heart of the HAICT method is the use of artificial stimuli that can be precisely controlled in ways that real medical images cannot be. Thus, as shown in Figure 2, the stimuli were 20x20 square grids in which each square was a shade of red or green.

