### **Specific Method**

We tested 13 naïve observers (avg age 31, 8 female, 5 male). All had normal color vision as assessed by Ishihara color plates and acuity of 20/25 or better.

Two conditions were be tested:

1. Baseline - No AI input. Observer classifies each case as "bad" or "not" bad on their own.
2. Second Reader - The observer makes an initial decision about every case. The simulated AI silently classifies stimuli using a "conservative criterion" ( $c = 0.5$ ). The logic for the conservative criterion is that the second reader is being used to cut down on false positive responses and so it is intended to raise questions about positive human responses that might be marginal. If the observer and AI disagree, then the AI informs the human observer. The observer is then given a chance to either change their response or go with their first opinion.

In each of these conditions, the prevalence of "positive cases" is varied in separate blocks. The percentage of targets could be 10%, 33%, 67% or 90%. Humans are known to become more conservative at low prevalence, missing more targets (Horowitz, 2017). Thus, there were 8 blocks per Observer (2 conditions X 4 levels of prevalence). Each Observer ran 200 trials in each block. Block order was randomized.

Stimuli were present in a darkened room on Macintosh desktop computers with Os at an approximate 60 cm viewing distance.

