## Data analysis

One observer was removed for poor performance. For the remaining 12 Os, we performed standard signal detection analysis. For each condition, we computed the probability of a “hit” or true positive response (correct positive responses / total positive trials) and “false alarms” or false positive response (false positive responses / total negative trials). These values are converted to “z-scores” (=inverse of the standard normal cumulative distribution), zHit & zFA. From those values,  $d'$  = zHit-zFA and criterion, ‘c’, = (zHit-zFA)/-2. Response time can also be looked at but is not of particular interest in this experiment.

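### d' and c come only from block totals; adjusting the hit and false-alarm rates for the known red-cell count, with one estimator in both conditions, would make them more precise with no new data

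*Protocol*

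**What the plan says.** The Protocol (item 3, Analyses) starts from block totals: "First, we summarize the number of hits, true negatives, misses, and false alarms in each block". Accuracy, positive predictive value, d' and criterion all follow from those. The combined protocol and SAP (Data analysis) reports the same approach: "For the remaining 12 Os, we performed standard signal detection analysis". There, hit and false-alarm proportions are formed for each condition and converted to z-scores. Neither document plans an analysis with a trial-level covariate.

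The stimulus value is nevertheless under the experimenters' control. HAICT methodology says: "At the heart of the HAICT method is the use of artificial stimuli that can be precisely controlled". The Figure 2 text explains how: "For a negative trial, the number of red cells is derived from one normal distribution", with a second distribution of higher mean for positive trials and a separation of d' = 2.5. In Second Reader blocks the program also classifies each case as the AI, because it has to compare that classification with the observer's first answer.

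On size, the Protocol states: "Observers will complete 20 practice trials and 200 test trials in each block". Prevalence is 10%, 33%, 67% or 90%. Thirteen observers were tested and twelve analysed ("One observer was removed for poor performance").

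**The concern.** At 10% prevalence a 200-trial block holds 20 positives, so the hit rate rests on 20 responses. At 90% the false-alarm rate rests on 20 negatives. A sizeable part of the error in such a rate is chance in which red-cell counts were drawn: 20 positives that happen to be redder than average give a high hit rate whatever the observer does. That part is known on every trial, and the planned totals ignore it.

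H1 (criterion against prevalence) and H3 (Second Reader at low prevalence) lean on these extreme blocks. With 12 observers, precision that can be had without further testing is worth taking. What is at stake is efficiency; the planned measures themselves are not wrong.

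**Working it through.** The documents give no standard error, power or sample-size figure for this point, so there is none to reproduce.

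**Inputs from the documents.** 200 test trials per block; prevalences 10/33/67/90%; 12 observers; stimulus separation 2.5; AI criterion c = 0.5 and AI d' 2.2 (Protocol).

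**Assumptions, not in the documents.** Human d' 2.0; c = +0.5, +0.2, -0.2, -0.5 from the lowest to the highest prevalence; 0-3% lapses (responses unrelated to the stimulus); between-observer SD of a contrast (tau) as stated.

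**1. Precision of block totals.** With hit rate H on nP positives and false-alarm rate F on nN negatives,

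Var(d') = H(1-H)/(nP·φ(zH)²) + F(1-F)/(nN·φ(zF)²), and SE(c) = SE(d')/2.

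| Prevalence | nP / nN | H | F | SE(d') | SE(c) |
|---|---|---|---|---|---|
| 10% | 20 / 180 | 0.691 | 0.067 | 0.327 | 0.163 |
| 33% | 66 / 134 | 0.788 | 0.115 | 0.224 | 0.112 |
| 67% | 134 / 66 | 0.885 | 0.212 | 0.224 | 0.112 |
| 90% | 180 / 20 | 0.933 | 0.309 | 0.327 | 0.163 |

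At 10% the two variance terms are about 0.086 (hits) and 0.021 (false alarms). The 20 positives therefore carry 0.086/0.107, about 80% of the variance of d'.

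**2. Adjusted rates.** Fit a probit of the response on red-cell count within observer and block. Then

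adjusted H = mean over positive trials of (response - fitted probability) + model mean over the known positive distribution,

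and likewise for F over negatives. The residual term keeps the rate close to correct when the probit is imperfect. In simulated blocks at 10% prevalence:

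- RMSE of d': about 0.30-0.34 from totals, 0.21-0.29 adjusted (a cut of roughly 12-32%).
- RMSE of c: about 0.16-0.18 from totals, 0.11-0.15 adjusted (roughly 12-33%).
- Absolute bias of the adjusted estimates: at most 0.05.

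**3. The pure probit as an alternative.** Taking d' = 2.5/√(1+noise²) directly from the fit gives an RMSE of about 0.12 at 10% prevalence if the model is exactly right. With 3% lapses, d' is biased by -0.14 to -0.18 at 10% prevalence. The H1 contrast (c at 10% minus c at 90%) gains a bias of about +0.07 against a group SE of 0.046. With 5% lapses the gain in d' can vanish.

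**4. Second Reader needs the AI term.** The final answer depends on the AI as well as the stimulus. If the AI has its own stimulus, a pure model on red-cell count alone biases final d' by -0.29 to -0.74 over the settings tried. The working model for final responses therefore needs count, AI classification and their product.

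**5. Group level.** Group SE = √(s² + tau²)/√12, with s the per-observer sampling SD. As an illustration, apply the per-block cuts of step 2 to s from totals, assuming that they hold in every block of the contrast.

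H1, c at 10% minus c at 90%, s = 0.228 from totals, so 0.201 to 0.153 after cuts of 12% and 33%:

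| tau | SE, totals | SE, adjusted | Cut |
|---|---|---|---|
| 0 | 0.066 | 0.044-0.058 | 12-33% |
| 0.3 | 0.109 | 0.097-0.104 | 4-11% |
| 0.5 | 0.159 | 0.151-0.156 | 2-5% |

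H3, Second Reader minus Baseline d' at 10% less the same at 90%, s = 0.674 from totals, so 0.593 to 0.458 after cuts of 12% and 32%:

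| tau | SE, totals | SE, adjusted | Cut |
|---|---|---|---|
| 0 | 0.195 | 0.132-0.171 | 12-32% |
| 0.3 | 0.213 | 0.158-0.192 | 10-26% |
| 0.6 | 0.261 | 0.218-0.244 | 6-16% |

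**The case against.** Block-total d' and c are the standard measures, they depend on no psychometric model, and H1 is a replication with a large expected effect. If the criterion shift is half of ideal at d' 2.1, the slope of c on log-odds of prevalence is about -0.5/2.1 = -0.24. A per-observer sampling SD of 0.050 gives a group SE of 0.050/√12 = 0.0144, so z is about 17 from totals. With a between-observer slope SD of 0.1, z is still 0.24/(√(0.050² + 0.1²)/√12), about 7.4. This stands: the documents give no sign that H1 is short of precision.

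A reader might infer that a trial-level probit could simply replace the planned measures, at no cost and with d' errors near 0.12. That does not hold. The figure needs an exactly correct model without lapses. A single noise value with a fixed separation also builds in the equal variance that H2 sets out to test. Using the pure probit in Baseline and adjusted rates in Second Reader would subtract estimators with different biases: with an AI of no effect and an assumed 3% lapses, this creates a spurious benefit of about +0.20 d' at 10% prevalence. Residual-adjusted rates in both conditions avoid that mismatch, and their small bias does not rely on the probit being exact.

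It is also fair to object that the documents do not say that counts or AI classifications were stored, do not state whether the AI saw the same stimulus in this experiment, and describe cells as shades of red or green, so the count may not be all the evidence on a trial. The storage point decides feasibility. The others affect how much is gained.

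**Conclusion.** The point holds as a matter of efficiency. Both documents discard a covariate that the program sets on every trial, and a robust adjustment for it would cut the per-block error of d' and c at 10% prevalence by roughly 12-33%. This rests on an assumed human d' of 2.0 and lapses of 0-3%. At group level the gain depends on how much observers differ: under the illustration above, as little as 2-5% for H1 at tau 0.5, and 6-16% for H3 at tau 0.6.

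The documents do not support the stronger inference that the planned d' and c are invalid, or that H1 or H3 cannot be tested without the change. The case resembles adjusting for a known covariate: worth doing, and cheap if the data exist.

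**What to change.** Add to the analysis section of both documents:

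1. For Baseline and Second Reader alike, estimate residual-adjusted hit and false-alarm rates per observer and block. The working probit uses red-cell count for unaided responses, and red-cell count, AI classification and their product for final Second Reader responses. The model mean is taken over the known stimulus (and AI) distribution.
2. Derive d' and c from these rates for H1 and H3, and report the raw block-total d' and c beside them. Do not make the pure probit d' the main estimate.

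Three things come first. Confirm that red-cell counts and AI classifications were logged or can be regenerated. Reconcile the AI d' of 2.2 in the Protocol with the SAP's statement under Figure 2 ("In this experiment, both the AI and human have a maximum performance of a" d' of 2.5), and state whether the AI had its own stimulus, before the AI term is modelled. Correct the criterion formula in the SAP's Data analysis: as printed, (zHit-zFA)/-2 equals -d'/2, which is -1.00 at all four prevalences when d' is 2.0. The usual form, -(zHit+zFA)/2, returns +0.50, +0.20, -0.20 and -0.50 under the assumptions above.

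The cost is analysis code, a few sentences of text and reliance on a working model. No new observers or trials are needed.

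### Must the zROC slope test name its condition and response before H2 can be judged?

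*Protocol*

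**What the plan says.** The Protocol's second hypothesis reads "We predict that the slope of the resulting zROC will be 1.0". Its Background introduces that curve while discussing the basic task: equal variance is expected there, prevalence will be varied to move the criterion, and this will trace an ROC. Only then does it add "We will also test the Second Reader faux-AI in order to determine if low prevalence makes Second Reader worse", which corresponds to H3.

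Section 3 (Analyses) computes accuracy, positive predictive value, d' and "the criterion for each observer under each of the different conditions". It continues "Given measures of performance at 4 levels of prevalence, we can estimate the ROC curve", adds the zROC, and states the test: "We will test the hypothesis that the slope of the zROC is equal to 1 (the consequence of an equal variance 2AFC task".

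Under section 2 (Conditions), the Second Reader observer decides first and is told if the AI disagrees. Then: "The observer is then given a chance to either change their response or go with their first opinion".

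The Combined protocol and SAP confirms in Specific Method that both conditions cover all four prevalences: "Thus, there were 8 blocks per Observer (2 conditions X 4 levels of prevalence". Its Data analysis section says "For the remaining 12 Os, we performed standard signal detection analysis. For each condition, we computed the probability of a" hit and of a false alarm, converts both to z-scores, and derives d' and c. It mentions neither a zROC nor a slope.

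**The concern.** Both AI rules are run at all four prevalences, so a reader who carries the per-condition scoring into the next sentence obtains two zROCs, while H2 makes one prediction. A Second Reader trial can also hold two responses, and neither document says which is scored.

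The choice is not neutral. Baseline responses and initial Second Reader responses are the observer's own decisions. Final Second Reader responses mix those decisions with an AI stated to work at a fixed criterion of c = 0.5. As prevalence moves the human criterion, the AI's rates stay put, and the mixture bends the zROC. The Protocol's Background treats a slope below 1, typically about 0.6, as the classic sign that signals vary more than noise. A final-response slope could look like that sign with no difference in variance. H2 could then face two disagreeing slopes with no stated rule for which decides, and the later document does not resolve this because it contains no slope test.

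**Working it through.** **Inputs from the documents.** Prevalences 10, 33, 67 and 90%; AI criterion c = 0.5; AI d' 2.2 (Protocol, end of section 2) or a maximum of 2.5 (Combined document, HAICT methodology); predicted slope 1.0.

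**Assumptions not in the documents.** Human d' 2.0 or 2.2; criterion shift 50, 75 or 100% of the ideal; human-AI correlation 0 or 0.5; all revision behaviour. With the two AI values this makes 2 × 3 × 2 × 2 = 24 settings.

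**Step 1: reproduce the predicted slope.** Human criterion c = shift × ln((1−p)/p)/d'. Hit = Φ(d'/2 − c), FA = Φ(−d'/2 − c). Example with d' = 2.0 and a 50% shift:

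| Prevalence | c | Hit | FA | zHit | zFA |
|---|---|---|---|---|---|
| 10% | 0.549 | 0.674 | 0.061 | 0.451 | −1.549 |
| 33% | 0.177 | 0.795 | 0.120 | 0.823 | −1.177 |
| 67% | −0.177 | 0.880 | 0.205 | 1.177 | −0.823 |
| 90% | −0.549 | 0.939 | 0.326 | 1.549 | −0.451 |

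zHit − zFA = 2.0 in every row, so the slope is 1.00. The same holds in all settings, for Baseline and for initial Second Reader responses.

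**Step 2: final responses, reversal regardless of confidence.** If a share q of all disagreements is reversed, final rate = human rate − q·P(human yes, AI no) + q·P(human no, AI yes) = (1−q) × human rate + q × AI rate, whatever the correlation. With AI d' = 2.2, AI hit = Φ(1.1 − 0.5) = 0.726 and AI FA = Φ(−1.1 − 0.5) = 0.055. At q = 0.2 in the example:

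- Hit at 10% prevalence: 0.8 × 0.674 + 0.2 × 0.726 = 0.684. The four hit rates are 0.684, 0.781, 0.849 and 0.897.
- FA at 90% prevalence: 0.8 × 0.326 + 0.2 × 0.055 = 0.272. The four FA rates are 0.059, 0.107, 0.175 and 0.272.
- Least-squares slope of zHit on zFA: 0.82.

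**Step 3: final responses, reversal only near the criterion.** The observer adopts the AI's answer only when the evidence lies within m SD of the observer's own criterion.

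**Results over the 24 settings, variances exactly equal:**

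| Revision behaviour | Slope |
|---|---|
| None (Baseline or initial) | 1.00 |
| Regardless of confidence, q = 10% | 0.86–0.91 |
| q = 20% | 0.78–0.84 |
| q = 30% | 0.72–0.77 |
| q = 50% | 0.60–0.64 |
| Near criterion, m = 0.25 SD | 0.92–0.98 |
| m = 0.5 SD | 0.84–0.94 |
| m = 1.0 SD | 0.77–1.01 |

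The technical point holds: a final-response slope reflects revision behaviour and cannot be read as a variance ratio. Its size depends on the behaviour assumed. The two m = 0.25 and m = 0.5 rows reverse about 15–19% and 28–35% of disagreements, yet give slopes closer to 1 than the confidence-blind rows at 20% and 30%.

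**Step 4: does the text leave H2 open?** Set side by side, the Background describes one curve for the basic task and then brings in Second Reader as an additional purpose. H2 speaks of one resulting zROC. Section 3 builds one curve from four prevalence levels, although there are eight blocks. The explanation attached to the test, equal variance of signal and noise, concerns the stimulus and the unaided decision. All of this points to Baseline.

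**The case for a change.** The strongest opposing case runs as follows. Section 3 is headed as a request for exact analyses, and the slope test is its only explicit hypothesis test. The Background describes the paradigm as one in which an AI can also help, so the basic task is not labelled unaided in so many words. H3 compares Second Reader with Baseline and would naturally use final responses, so the hit and false-alarm rates for a misleading slope would already be to hand. Two or three sentences would close the gap.

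The omission is real, and so is the warning against reading a final-response slope as evidence on variance. Three things limit what follows.

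- The two-slope conflict needs the per-condition scoring to be carried into a sentence that describes one curve, against the order of the Background.
- Specific Method and Data analysis are in the past tense: 13 observers tested, one removed, 12 analysed. A clarification now would be a label added afterwards, without the protection of pre-specification.
- Naming Baseline would not by itself secure the test. The extreme blocks hold only 0.10 × 200 = 20 signal or 20 noise trials. Simulated Baseline least-squares slopes with a true value of 1 had medians of 0.81 to 0.97 (assuming human d' 2.0 or 2.5, a shift of 50 or 100%, and a 0.5/1 count correction). The estimator is a separate matter.

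The missing slope test in the Combined document does not contradict the Protocol. That document computes zHit and zFA, which are the inputs to the slope, and says nothing against fitting it.

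**Conclusion.** No change to the plan is needed. H2 names neither condition nor response, but the Background's order and the single curve in section 3 lead an analyst to the unaided task, and the Baseline data for that test exist under every reading. The harm arises only if someone fits final Second Reader responses and reads the slope as a variance ratio. In that case the slope would be about 0.6 to 0.9 under confidence-blind reversal of 10 to 50% of disagreements, or about 0.77 to 1.01 under near-criterion reversal, against 1.00 for unaided responses. These ranges rest on assumed human d', criterion shift, correlation and revision behaviour. They illustrate the mechanism and do not estimate what this study would show. Anyone who reads the results should treat a final-response slope as descriptive.
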